7.7 DETERMINATION OF SAMPLE SIZE

Based on previous experience with empagliflozin it is estimated that the change in HbA_{1c} from baseline after 26 weeks of treatment is 0.3% in empagliflozin (2.5 mg, 10 mg and 25 mg) and 0% in placebo and that the standard deviation of this difference is 0.9%.

As this trial investigates primarily the 2 higher dose levels of empagliflozin, 10 mg and 25 mg, the alpha (Type I error) is assumed to be 2.5%. Assuming that the change from baseline in HbA_{1c} follows a normal distribution (Student's t-test) and that a two-sided test will be employed, with equal standard deviations, then a sample size of 225 patients per arm will show superiority with a power of 90%.

Based on the results of these 2 tests (see Section 7.2 for further details), when comparing empagliflozin 2.5 mg (n=225) to placebo (n=225) on the primary endpoint, there is 82% power, respectively 76%, to detect a significant difference (alpha=1%, respectively alpha=0.5%) of 0.3% with a common standard deviation of 0.9%.

Software package nQuery version 7.0 was used to derive the sample size.

Given that there are 4 treatment groups, a total sample size of 960 patients (240 per group) will be randomised to allow for an estimated 6% of patients who do not qualify for the FAS.

Page 88 of 122

Proprietary confidential information © 2016 Boehringer Ingelheim International GmbH or one or more of its affiliated companies

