7.8.2 Laboratory data

For continuous safety laboratory parameters standardised and normalised values will be derived as well as the differences to baseline. The process of standardisation and normalisation as well as standard analyses for safety laboratory data are described in the BI guidance for the Display and Analysis of Laboratory Data (10). All analyses considering multiple of times upper limit of normal (ULN) will be based on original and not normalized data.

The analyses of laboratory data will be descriptive in nature and will be based on BI standards.

Results of laboratory analyses will be presented based on both SI units and US conventional units.

Baseline for safety laboratory parameters will be the last available measurement before the start of randomised study drug. In general, laboratory measurements taken up to 3 days after the last administration of randomised study drug will be considered as on-treatment. The exception will be for the liver enzyme elevation analysis (see below).

Only patients with at least one available on-treatment value will be included in the analysis of an individual laboratory parameter. All individual data will be presented in listings.

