7.8.2.5 Blood beta-hydroxybutyrate (BHB)

Refer to [Section 6.7](#) for the baseline definition of BHB endpoints.

- Serum BHB sampled at the site and analysed at the central laboratory

All the analyses described for this endpoint will be performed on fasted measurements only.

Descriptive statistics for baseline, actual values and change from baseline over time will be calculated. Descriptive statistics will also be provided to characterize the follow-up period.

The median and the corresponding confidence interval using SD will be plotted over time including the follow-up period. A box-plot presenting the value at baseline and over time will also be produced per treatment group.

A shift table from baseline to last value on treatment, (and from baseline to maximum value on-treatment) will also be provided by baseline values (<0.6 mmol/L, 0.6 to ≤ 1.5 mmol/L, >1.5 to <3.8 mmol/L, ≥ 3.8 to ≤ 8.0 mmol/L, > 8.0 mmol/L).

An additional shift table will display the number of patients in these BHB categories over time.

- Capillary self-measured BHB via the ketone meter and reported in the diary

Elevated ketone readings above >1.5 mmol/L that have not been confirmed by the investigator will not be included in any analysis of this section. Refer to [Section 5.4.6.1](#) for further details on the ketone reading confirmation process.

Morning and daily endpoints

For all analyses specified in this section, capillary BHB readings reported as “HI” will be imputed to 8.1 mmol/L.

The periods of time of interest will be the following ones: week 1, week 2, week 3, week 4, week 5 to week 6, week 7 to week 8, week 12, week 18, week 22 and week 26.

Descriptive statistics will be produced on the average of morning BHB measurement values over the specific periods of time defined above.

The same descriptive statistics will be produced on the average of daily BHB measurement values over time, using the same periods of time defined above.

High BHB measurements

The analysis described in this paragraph will focus on high BHB measurement values that a patient may have reported in the diary. For this analysis, "HI" readings will be considered as such and not be replaced by a numerical value (for instance 8.1 mmol/L).

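### The SAP builds the plotted confidence interval for median serum BHB from the SD, which does not measure the sampling error of a median

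*SAP*

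**What the plan says.** SAP 7.8.2.5 covers serum BHB sampled at the site and measured centrally. It restricts the data: "All the analyses described for this endpoint will be performed on fasted measurements only". It then specifies the figure at issue: "The median and the corresponding confidence interval using SD will be plotted over time including the follow-up period". No confidence level, multiplier, standard-error formula or transformation is given there, and nothing in the readable SAP text supplies one. SAP section 7 provides geometric statistics for variables analysed on the log scale but does not place BHB among them.

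Other displays of the same variable follow. One is graphical: "A box-plot presenting the value at baseline and over time will also be produced per treatment group". Shift tables use the categories "<0.6 mmol/L, 0.6 to ≤ 1.5 mmol/L, >1.5 to <3.8 mmol/L, ≥ 3.8 to ≤ 8.0 mmol/L, > 8.0 mmol/L". SAP 7.8.2 sets the status of all this work: "The analyses of laboratory data will be descriptive in nature and will be based on BI standards".

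**The concern.** An interval built from the SD of the observations belongs to a mean. Its half-width is a multiple of SD/√n because that is the standard error of a mean. The sentence attaches this quantity to a median, whose standard error is a different one. A programmer following it must guess a formula, and none of the obvious guesses gives a 95% interval across plausible shapes of the data.

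Ketones matter in this trial. The protocol (2.3 and 5.3.2.2) says that a mild to moderate rise may occur through the drug's mechanism, and 5.3.6.1 lists diabetic ketoacidosis as an adverse event of special interest. Readers will use the error bars to judge how precisely each arm's median is known at each visit, so the bars should mean what their label says.

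**Working it through.** The plan states no figure here, so there is nothing to reproduce. The check is of the method.

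**Inputs.** n = 225 per arm, the evaluable number in Protocol 7.7, with 240 (the number randomised per arm) as a check. Assumed, because the documents do not give them: a 95% level; either a normal shape or a log-normal shape with log-SD s = 0.5, 0.75 or 1.0.

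**Theory.** For large n, SE(median) = 1/(2 f(m) √n), where f(m) is the density at the median m.

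- Normal data: SE(median) = 1.2533 × SD/√n.
- Log-normal data: f(m) = 1/(m s √(2π)), so SE(median) = 1.2533 × s × m/√n, while SD = m × exp(s²/2) × √(exp(s²) − 1).

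Let R be SD/√n divided by the true SE(median). The approximate coverage of median ± 1.96 SD/√n is then 2Φ(1.96 R) − 1. The simulated coverage and width below come from 20,000 samples per case at n = 225; width is relative to the order-statistic interval.

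| Shape | SD | R | Large-sample coverage | Simulated coverage | Relative width |
|---|---|---|---|---|---|
| Normal | – | 1/1.2533 = 0.798 | 88.2% | about 88% | about 0.78 |
| Log-normal, s = 0.5 | 0.604 m | 0.604/0.627 = 0.964 | 94.1% | about 94% | about 0.93 |
| Log-normal, s = 0.75 | 1.151 m | 1.151/0.940 = 1.225 | 98.4% | about 98% | about 1.17 |
| Log-normal, s = 1.0 | 2.161 m | 2.161/1.253 = 1.724 | 99.9% | about 99.5% | about 1.62 |

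At n = 240 the simulated coverage is 88.0% (normal), 93.7% (s = 0.5) and 99.6% (s = 1.0), so the choice of n hardly matters.

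**Adding the normal-theory factor.** Median ± 1.96 × 1.2533 × SD/√n covers 95.0% for normal data, but 98.0% at s = 0.5 and 99.9% at s = 1.0 (n = 225). It repairs the normal case only.

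**Plain SD.** Median ± SD does not shrink with n and covered the true median in 100% of samples. In population terms its lower limit is:

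- s = 0.5: (1 − 0.604) m = +0.396 m
- s = 0.75: (1 − 1.151) m = −0.151 m
- s = 1.0: (1 − 2.161) m = −1.161 m

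The limit is therefore an impossible concentration in the last two cases but not in the first.

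**Sensitivity to one extreme value.** Take n = 240, s = 0.5 and an assumed median of 0.2 mmol/L, then set one patient to 8.0 mmol/L. The mean full width of the SD/√n interval rises from 0.030 to 0.131 mmol/L (4.3-fold). The order-statistic interval stays at 0.032 to 0.033. The median resists an outlier; the SD does not.

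**A valid interval.** At n = 225 the 98th to 128th ordered values cover the median with probability P(98 ≤ B ≤ 127), where B is binomial(225, 0.5). This is 95.5% for any continuous distribution. At n = 240 the 105th to 136th values also give 95.5%.

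**The case against.** The strongest reply is that the sentence may be loose wording. The SAP does not write SD/√n, so every coverage figure above tests a formula supplied by this review, and a mean with an SD-based interval may have been meant. That stands as a limit on the numbers. It does not rescue the text: median and SD are mismatched as written, and the statistic or the interval has to change.

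A second reply is that skewness is not documented. That is correct. The shift-table categories also serve maximum on-treatment values, so they do not describe the distribution at a visit, and at log-SD 0.5 the plain formula happens to be close to nominal. The defect does not depend on skew, however, since the same formula covers only about 88% for normal data.

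A third reply is that a distribution-free display is already planned. The box-plot normally shows the median and quartiles, and SAP section 7 puts Q1, median and Q3 in the end-of-text tables. This also stands, and it limits the consequence.

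A reader might go further and infer that this is the principal ketone display and that its bars would hide a difference between the active arms and placebo. The documents support neither inference. The SAP does not rank this figure above the others. Bars are too wide only under strong skew or with outliers, and per-arm intervals are not a between-arm test. Ketone risk is also assessed through adjudicated ketoacidosis, Kaplan-Meier curves with log-rank tests, and ketosis episodes (SAP 7.8.1.4), none of which uses this plot.

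**Conclusion.** The point holds as a method error in one figure. An SD-based interval is not a generally valid confidence interval for a median, and the readable SAP text does not correct or complete the instruction. That conclusion rests on the sampling theory of the median alone.

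The size is conditional. Under median ± 1.96 SD/√n, coverage of a nominal 95% interval runs from about 88% to 99.5% over the shapes tried, and the direction of the error depends on skew. Those figures assume the formula, the 95% level and the normal or log-normal shape. The number of fasted samples at each visit is also unknown.

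The importance is low: the figure is descriptive, other displays of the same data are planned, and the primary and key secondary analyses are untouched.

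**What to change.** In SAP 7.8.2.5, drop the reference to the SD and state the level and method: median by visit and treatment group with a distribution-free (binomial order-statistic) 95% confidence interval. This works at whatever number of fasted samples each visit yields. Alternatively, plot the median with Q1 and Q3 and label the bars as quartiles, not as a confidence interval. If a mean was intended, name the mean instead.

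The cost is one phrase in the SAP and a small change to the plotting program. No new data are needed and no other analysis changes.

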7.8.2.6 Urine ketone

Refer to [Section 6.7](#) for the baseline definition of urine ketone endpoints.

The analyses described for this endpoint will be performed on fasted measurements only.

Analysis of categorical urine ketone data (negative, trace, 1+/small, 2+/moderate, 3+/large, 4+/large+) will be performed by value at baseline, over time, and worst value on treatment. The analysis will be presented as frequency table and graphically on pie charts.

7.8.3 Vital signs

Other than the analysis of SBP and DBP as key secondary endpoints, only descriptive statistics are planned for the summary of pulse rate (bpm) and change from baseline in pulse rate over time based on the treated set (OC, OC-AD).

7.8.4 ECG

12-lead ECG measurements will be taken at baseline (visit 6) and at EOT (visit 11). ECG-findings before first intake of trial drug will be considered as baseline condition. Any clinically significant new findings in the ECG measurement after the first ECG will be considered as AEs and analysed as planned in [Section 7.8.1](#).

7.8.5 Others

Not applicable

9 ADDITIONAL SECTIONS

[REDACTED]

[REDACTED]

[REDACTED]

[REDACTED]	[REDACTED]
[REDACTED]	[REDACTED]
[REDACTED]	[REDACTED]
[REDACTED]	[REDACTED]
[REDACTED]	[REDACTED]
[REDACTED]	[REDACTED]
[REDACTED]	[REDACTED]

9.2 SPECIAL SEARCH CATEGORIES AND ATC LEVELS FOR CONCOMITANT MEDICATION

The defining ATC levels and ATC codes of the WHO DD special search categories for the use of antihypertensives, ASA and lipid lowering drugs and are shown in Table 9.2:1.

Medications in the categories C02, C03, C07, C08 and C09 that have a missing ATC3 code will also be considered antihypertensives and will be presented in the respective table by their preferred name under antihypertensives.

[figure not shown]
Table 9.2: 1 WHO DD special search categories

[figure not shown]
WHO DD special search categories			
SSC	Displayed category	ATC level	ATC code
ASA	ASA	ATC4	B01AC
Antihypertensives	Antiadrenergic agents, centrally acting	ATC3	C02A
	Antiadrenergic agents, ganglion-blocking	ATC3	C02B
	Antiadrenergic agents, peripherally acting	ATC3	C02C
	Arteriolar smooth muscle, agents acting on	ATC3	C02D
	Other antihypertensives excluding magnesium and magnesium sulfate	ATC3	C02K*
	Antihypertensives and diuretics in combination	ATC3	C02L
	Combinations of antihypertensives in atc-gr. C02	ATC3	C02N
	Low-ceiling diuretics, thiazides	ATC3	C03A
	Low-ceiling diuretics, excl. thiazides	ATC3	C03B
	High-ceiling diuretics	ATC3	C03C
	Potassium-sparing agents	ATC3	C03D

[figure not shown]
* C02K excluding the terms magnesium and magnesium sulphate

WHO DD special search categories (cont.)

SSC	Displayed category	ATC level	ATC code
	Diuretics and potassium-sparing agents in combination	ATC3	C03E
	Other diuretics	ATC3	C03X
	Beta blocking agents	ATC3	C07A
	Beta blocking agents and thiazides	ATC3	C07B
	Beta blocking agents and other diuretics	ATC3	C07C
	Beta blocking agents, thiazides and other diuretic	ATC3	C07D
	Beta blocking agents and vasodilators	ATC3	C07E
	Beta blocking agents and other antihypertensives	ATC3	C07F
	Selective calcium channel blockers with mainly vas	ATC3	C08C
	Selective calcium channel blockers with direct car	ATC3	C08D
	Non-selective calcium channel blockers	ATC3	C08E
	Calcium channel blockers and diuretics	ATC3	C08G
	ACE inhibitor, plain	ATC3	C09A
	ACE inhibitor, combinations	ATC3	C09B
	Angiotensin II antagonists, plain	ATC3	C09C
	Angiotensin II antagonists, combinations	ATC3	C09D
	Other agents acting on the renin-angiotensin system	ATC3	C09X
Lipid lowering drugs	Niacin	ATC4 [nicotinic acid and derivatives]	C10AD
	Fibrates	ATC4 [Fibrates]	C10AB
	Statins	ATC4 [HMG COA reductase inhibitors]	C10AA
	Other	Other lipid modifying agents	C10AX
		Bile acid sequestrants	C10AC

10 HISTORY TABLE

Table 10: 1 History table

Version	Date	Author	Sections changed	Brief description of change
Final	17-MAY-17	[REDACTED]	None	This is the final TSAP without any modification
Revised	11-OCT-17	[REDACTED]	
 [REDACTED] [REDACTED] 6.7 7.5.1.2 7.5.1.4 [REDACTED] 7.8.1.4 7.8.1.5 	
 • [REDACTED] • [REDACTED] • Follow-up period for the assignment to active treatment for hepatic injury added • Multiple imputation analysis for body weight and blood pressure adapted • [REDACTED] • Definition of ketosis episodes added • A negative binomial model will be fitted to analyse the symptomatic hypoglycaemia with PG < 54 mg/dL • Minor changes in the wording and correction of typos
